**Figure 1: Enhanced Replicating Effective Programs (REP) to Facilitate Implementation of CCMs**

**Enhanced REP:** In a recent implementation of REP (R01 MH79994), community-based administrators and providers made specific recommendations to the Technical Assistance component that would help develop a **business case** for the CCM based on organizational as well as financial incentives (73). This **Enhanced REP** framework includes ongoing assessment of organizational barriers or facilitators to implementation (11, 82-87) based on the **Organizational Transformation Model- OTM** (88) that assesses both context as well as organizational change factors that might influence implementation. The OTM assessment (72) measures organizational processes found to be associated with improved quality (89), including the practice's readiness to implement new programs (e.g., CCM), leadership commitment, degree to which frontline providers are involved in the operationalization of a new program, and alignment of new program goals with existing priorities and day-to-day processes. Enhanced REP emphasizes dissemination of data to health plan leaders and other stakeholders, and aligning CCM components with reimbursement strategies that may inform the implementation of emerging initiatives including accountable care organizations.

4. This proposal represents a true private-public partnership in light of other AHRQ initiatives (90). Community-based providers involved in our previous studies (R01 MH74509, MH79994) have strongly emphasized the need for CCMs across mood disorders from smaller practices (73). Aetna will provide all care management infrastructure, data, and staff while federal research funds are limited to support of training and evaluation. All products developed from this project will be made available in the public domain based on AHRQ guidelines. Finally, this R18 also addresses unanswered questions raised by a recent AHRQ report on setting a National Agenda for Research in Collaborative Care (2).

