**Training** for care managers will follow existing Aetna standard procedures for telephonic and web-based training. This will consist of 16 hours of telephonic training by [name] and her study team over 2 weeks modeled after our current on-site training package.

**Technical assistance** will be provided by the Joint Operating Committee and supported by study consultants [name] (telephonic care management) and [name] (implementation processes). Joint Operating Committee members will conduct conference calls with the care managers (weekly) and supervisors (monthly) to guide the use of CCM components, particularly with regard to interface issues between: care managers and patients; care manager and providers/practices; and patients and providers. The Joint Operating Committee will have separate quarterly and ad hoc calls with consultants for debriefing and advice.

**C.5.f. Data Collection and Measures.** Key outcomes data will be ascertained from patients (including surveys, medical record- eTUMS reviews, and claims data) and organizational surveys (Table 5).

**Patient survey:** A concise (15-30 minute) quantitative survey will be collected from patients via phone at baseline, 6, 12, 18, and 24 months thereafter by the research associate (RA). If the RA is unable to reach the patient via phone for follow-up assessments after multiple attempts, a survey will be mailed to the confirmed last known address of the participant as a final attempt to receive this data. Patients will be asked to return this survey without any identifying information on the survey or the envelope. The survey will contain a subject ID number to identify the patient’s survey when it is returned via mail. Patient outcomes data will be entered by the RA into a database on a password-protected research computer within a secure network server at the University of Michigan.

**Patient utilization and cost data,** described below will be ascertained from the Aetna eTUMS and claims databases, and exported securely for merging with survey data and analysis at the University of Michigan.

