**Table 5: Primary and Secondary Outcomes and Measures – Baseline and Follow-ups**

Aims	Key Measures	Source
Aim 1. Primary outcomes	Mood symptoms: PHQ-9	Patient survey
	Health-related quality of life-SF-12	Patient survey
Aim 1. Secondary outcomes	Guideline concordant care- key measures	Medical record (eTUMS)/claims
	Mood tx: % receiving guideline-concordant antidepressants (if unipolar depression) or guideline-concordant anti-manic treatment (bipolar disorder dx) in 6-month period	Medical record (eTUMS)/claims
	Cardiometabolic monitoring: % receiving lipid profile, fasting glucose or HbA1C	Medical record (eTUMS)/claims
	Hospitalizations (ACSC)	Aetna claims data
	Productivity (Work Limitation Questionnaire)	Patient survey
Aim 2	Organizational data: Practice demographics	Aetna data
	Patient: demographics, comorbidities	Patient survey
Aim 3:	CCM costs, patient inpatient, outpatient, ER, Rx use	Aetna claims, provider survey
	Patient utilities (SF-6)	Patient survey

**The research associate will be blind to random assignment at baseline.** In follow-ups, given the nature of the CCM intervention (CCM-2), there is the possibility that enrolled patients may inadvertently disclose their randomization status with the RA. In pilot studies we found that this is a rare occurrence, but will be mitigated through RA training (e.g., minimizing leading questions that would disclose treatment assignment).

**Primary Aim 1 (patient-level quality of life, symptoms)** include changes in mood symptoms based on the PHQ-9 (102, 103) or ISS (52, 104-106) and health quality of life via the SF-12 Mental and Physical Health Component Scores (**MCS/PCS**; 85,113).

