**Aim 3: Utilization, costs, CEA, and business case:** Primary utilization measures of interest, including outpatient services, inpatient (including length of stay), and ER use, and health care costs will be ascertained from Aetna eTUMS electronic record reviews using a standard assessment tool (125). Cost data will be estimated for each inpatient, ER, and outpatient visit using Current Procedural Terminology (CPT) codes. A relative value unit (RVU) weight will allow for the use of the Medicare Fee Schedule to calculate a standardized cost for each service. Costs incurred in different years will be discounted at an annual rate of 3% and adjusted for inflation and discounted to the baseline (first) year of the study. Other costs incurred by the participants including medications, visit co-pays, transportation, and time involved in the CCM will be ascertained from the

patient survey. CCM cost data will be estimated using a time-motion survey developed by study investigators (R01 MH 79994) administered monthly to the CMs and quarterly to providers over a 2-year period, which ascertains time spent on CCM activities, including self-management, phone contacts, and documentation.

**C.5.g. Analyses.** General approach: The principal analyses will be for the primary hypotheses. An intent-to-treat analysis will be performed for all analyses. Bivariate baseline analyses will first be conducted to see if randomization was successful by comparing patient demographics and clinical characteristics (e.g., mental health diagnoses) between randomization groups. If there is a lack of equal distribution across groups, these variables will be added as covariates to analyses or propensity scoring will be used. Baseline characteristics will be compared among those enrolled but dropped out over time to those who remained in the study. Our unit of analysis for patient-level outcomes will be patients nested within practices with an indicator for non-solo practice provider sites (126, 127) and an indicator for patients diagnosis (bipolar vs. unipolar depression).

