**Aim 2 analyses are considered exploratory** but will be used to gain insight into the mechanisms by which CCM impacts patient outcomes. We will first explore the strength and direction of the association between patient-level CCM engagement (API-D scores- see section C.5.f) (119) on changes in outcomes (SF-12, PHQ-9 and ISS scores) by adding patient-level API-D scores to the aforementioned linear mixed-effects models from Aim 1. We will also be run exploratory analyses in which we add key organizational factors (e.g., non-solo practice, practice type-primary care vs. behavioral health, presence of non-MD clinical staff, EMR use, ownership), and other patient factors (e.g., demographics, comorbidities) in the models specified in Aim 1. In secondary analyses we will also incorporate the number of additional optional sessions covering supplemental modules completed by the patient (Section C.5.d).

**Aim 3: Both a payer and societal-based cost-effectiveness analysis (CEA) will be conducted.** A CEA from the payer perspective will involve comparison of utilization costs of health service providers including CM's time ascertained from time-motion survey. A societal perspective will add non-health care costs incurred by patients including time and transportation. Generalized Linear Models with log link functions will be used to correct for heteroscedasticity and reduce the impact of outliers (131). The incremental effectiveness of CCM compared to EC will be measured by changes in health utilities, assessed using a method described by Zivin (132) and Brazier (133) which translates six of the SF-12 items to changes in health utility (SF-6) based on responses to standard gamble questions given by community members regarding all combinations of possible health states. Cost-effectiveness ratios will be calculated based on the difference in per patient costs and effectiveness of CCM versus EC. To quantify uncertainty around these ratios, a standard nonparametric

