**C.5.I. Dissemination and Generalizability.** A dissemination strategy that ensures awareness and knowledge of research findings among clinicians, consumers, and policymakers, is an initial step to realizing the promise of this project, and fostering the potential generalizability of the findings. Once the intervention is completed and if proven effective, the Enhanced REP Framework will be applied to train other Aetna care managers in CCM. There are three stages of REP (packaging, training, and technical assistance). The CCM package will consist of a web-based therapist manual, administrator overview, and consumer handouts. Care managers as part of this study as well as providers with a high uptake score will be encouraged to become mentor-trainers who can provide training for other providers in the CCM. A refined technical assistance program based on study findings will be incorporated into the business plan for sustaining CCMs across Aetna and elsewhere. Study findings as well as the business plan will be disseminated through web sites, press releases, national conferences, policy briefs, as well as traditional forms of academic scholarship. If proven effective, the telephonic mood disorders CCM program may also potentially be scaled up to larger practices, notably through the use of technologies such as telemedicine or web-based portals independent of the care manager's physical location. At least five manuscripts will be produced based on study aims including: 1) description of the Aetna CCM, and 2) CCM main outcomes, 3) mechanisms of CCM effects, 4) cost and utilization of CCM, and 5) the updated CCM business plan. A policy brief based on study findings will be disseminated to consumer and policy groups (e.g., AHRQ, CMS, Depression and Bipolar Support Alliance, National Alliance for the Mentally Ill, Primary Care Associations, National Council for Community Behavioral Healthcare), as well as to policymakers who have an interest in mental health.

1. U.S. Department of Health and Human Services. U.S. Department of Health and Human Services (HHS) Inventory of Programs, Activities and Initiatives Focused on Improving the Health of Individuals with Multiple Chronic Conditions (MCC): Compiled by the HHS Interagency Workgroup on Multiple Chronic Conditions under the direction of [name], MPH, Deputy Assistant for Health (Science and Medicine), Office of the Assistant Secretary for Health; September 2011 Contract No.: Document Number|.

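### CCM programme cost is measured only through care-manager and provider time, so training, technical assistance, added supervision and web-platform costs have no stated measurement and the business-case return would look too favourable

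*Combined protocol and SAP*

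**What the plan says.** Section C.5.f (Aim 3 paragraph) takes CCM cost from a time-motion survey "administered monthly to the CMs and quarterly to providers over a 2-year period". The survey is one "which ascertains time spent on CCM activities, including self-management, phone contacts, and documentation". Table 5 gives the source of the Aim 3 cost data as "Aetna claims, provider survey". In C.5.g the payer analysis adds to utilization costs the care manager's "time ascertained from time-motion survey". C.5.f also collects "Other costs incurred by the participants including medications, visit co-pays, transportation, and time involved in the CCM", but these are participants' costs, not the cost of running the programme.

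Other sections describe further inputs:

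- **Training and technical assistance (C.5.e):** sixteen hours of training by the study team, weekly committee calls with care managers, monthly calls with supervisors, and consultant support.
- **Web programme (C.5.e, Packaging):** a web-based self-management programme used by care managers and patients.
- **Supervisor meetings (C.5.k):** weekly meetings with the care managers' supervisors, and health-plan effort given in kind.

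On funding, item 4 of section B (Innovation) states: "Aetna will provide all care management infrastructure, data, and staff while federal research funds are limited to support of training and evaluation".

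On use of the results, C.5.h puts a financial return to the health plan first in its definition of a business case. Table 6 lists trade-offs with initial investment. C.5.l plans to train further care managers and adds: "A refined technical assistance program based on study findings will be incorporated into the business plan".

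**The concern.** The people surveyed are not the people who supply training and technical assistance. Claims data will not reveal that effort either, because claims record services to patients. Grant-funded training and in-kind effort do not surface as plan expenditure. The plan therefore treats training and technical assistance as part of what is to be disseminated, without a stated way to cost them.

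The error would run in one direction. Every omitted input is a positive cost of the CCM arm, so leaving it out favours the CCM, and a larger sample does not reduce it. It matters most to another health plan, without the grant or the in-kind effort, that reads the business case to decide whether to adopt. Unlogged call hours are also hard to reconstruct afterwards.

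**Working it through.** The documents give no programme cost, wage or return-on-investment figure, so there is no figure of the plan's own to reproduce. Direction can be established by algebra; size can only be illustrated.

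**Direction.** Let B be gross saving, C the measured programme cost, and fC the omitted cost.

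- Net return: measured B - C; full B - C(1 + f). The measured value is too high by fC, whatever the sign of B.
- Return on investment: measured B/C - 1; full (B/C)/(1 + f) - 1. For positive B the measured value is too high, and the sign changes once f exceeds B/C - 1.

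**Scheduled contact hours (denominator).**

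- Ten sessions of 30 minutes and 12 monthly contacts (Table 4). The monthly contact is taken as about 15 minutes, the length that C.5.d gives for the clinical assessment.
- 172 patients in the CCM arm (C.5.i).
- 10 × 0.5 + 12 × 0.25 = 8 h per patient; 8 × 172 = 1,376 h.

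**Unsurveyed hours (numerator).** Assumptions: one group training with one trainer; calls of 0.5 to 1 h; one leader on each weekly call; two people (leader and supervisor) on each monthly call; delivery for 104 to 130 weeks. The upper end is 18 months' recruitment (C.5.k) plus 12 months' treatment, that is 30 months.

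| Input | Low | High |
|---|---|---|
| Trainer | 16 h | 16 h |
| Weekly call leader | 104 × 0.5 = 52 h | 130 × 1 = 130 h |
| Monthly calls | 24 × 0.5 × 2 = 24 h | 30 × 1 × 2 = 60 h |
| Total | 92 h | 206 h |
| Share of 1,376 h | 6.7% | 15.0% |

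**Sensitivity.**

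- If monthly contacts last 30 minutes, the denominator is (5 + 6) × 172 = 1,892 h, and the share is 92/1,892 = 4.9% to 206/1,892 = 10.9%. Documentation and ad hoc time would lower it further.
- If the weekly supervisor meetings in C.5.k count as programme cost, with two people at 0.5 to 1 h, they add 104 to 260 h. The total is 196 to 466 h, or 14% to 34% of 1,376 h.
- With one to three committee or consultant staff per technical-assistance call, 52 to 130 weeks and the supervisor meetings included, the total runs from 106 h to 786 h: 106/1,892 = 6% to 786/1,376 = 57%.

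**Effect on the return, at an assumed B/C of 1.5** (measured return on investment 0.50): f = 0.07 gives 1.5/1.07 - 1 = 0.40; f = 0.15 gives 0.30; f = 0.20 gives 0.25; f = 0.50 gives 0.00. A share in hours equals a share in cost only if average wages are equal and measured cost consists of scheduled contact alone. Consultant time and web-platform running cost are extra.

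**The case against.** The strongest reply is that this is a gap in specification rather than a wrong result. C.5.g announces a return-on-investment analysis without a formula or list of costs, and Table 6 shows that the authors have initial investment in mind. The budget justification and the business-case paper in the appendix are not available and may quantify some inputs. C.5.j calls the cost-effectiveness analysis exploratory, and Aim 1 is untouched.

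Much of this stands. A reader might infer that the return on investment is already overstated. The documents do not support that, since neither formula nor figure exists; only the conditional statement holds. The exploratory label concerns power, however, and does not remove a one-sided omission.

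A reader might also infer that care managers' own training and call time goes unrecorded. With two to three care managers that would add 32 to 48 h of training and 104 to 390 h of calls, giving 228 to 644 h, or 17-47%. The documents do not support this either. Care managers are the people surveyed, and the list of activities is open-ended. At the caseload of 80 to 100 in C.5.d, 172 patients need about two care managers (172/100 = 1.7; 172/80 = 2.2). With two, the upper total is 206 + 32 + 260 = 498 h, or 36%.

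Nor do the documents say that every input must be replicated. C.5.l names packaging, training and technical assistance, not supervisors, and mentions web portals as a possible route to larger practices. C.5.c shows that biweekly individual supervision and monthly team meetings already exist, so only added supervision counts. Part of the committee's work is trial management. Start-up training is a one-time cost that later patients would share. Grant-funded training is not a payer cost within the trial, so a delivery-only payer analysis is defensible if labelled.

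**Conclusion.** The concern holds as a conditional one. The only stated programme-cost instrument covers care-manager and provider time. Trainer time, committee and consultant technical assistance, added supervision and web-platform running cost have no stated measurement, although training and technical assistance are to be carried into dissemination and the business plan. If C.5.f is followed as written, programme cost would be understated and net return overstated, in favour of the CCM.

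The size cannot be determined from the documents. Roughly 7-15% of scheduled contact hours is an illustration that rests on assumed call lengths, staffing and duration, and on a denominator of scheduled contact alone. This should be corrected before cost collection starts; it does not bear on the clinical outcomes.

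**What to change.** In C.5.f and the Aim 3 rows of Table 5, beside the time-motion survey:

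- Log training, technical-assistance, added-supervision and consultant hours prospectively, separating programme support from trial management.
- Record the web platform's running cost.
- Confirm that the care-manager survey captures their own training and call time.
- Value in-kind and grant-funded effort at wage rates.

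In C.5.g and C.5.h, state the cost base for return on investment. Report programme cost and return both as delivery only and as delivery plus implementation, separate one-time from recurring cost, and treat past development as sunk. The trial's payer cost-effectiveness analysis may stay delivery-only if it is labelled so.

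The cost is a short log kept by the committee and trainers and a few extra cost lines. The downside is a less favourable return on investment.

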### **Our Specific Aims are to:**

1. Determine whether individuals with mood disorders treated with a health plan-level CCM demonstrate improved health outcomes and quality of care at 12 months compared to those who are mailed educational material alone (Educational Control-EC).

Our **primary hypothesis** is that compared to EC, the mood CCM will result in a) reduced mood symptoms in 12 months, or b) improved health-related quality of life.

Our secondary hypotheses is that patients receiving CCM vs. EC will have improved guideline-concordant care (e.g., mood disorders treatment, cardiometabolic monitoring), reduced hospitalizations, and improved work productivity within 12 months.

2. To support subsequent CCM dissemination by identifying key organizational, provider, and patient characteristics associated with CCM engagement and outcomes.
3. To conduct a cost-effectiveness analysis of CCM versus EC on changes in patient utilities over 24 months and apply findings to develop a business case for CCMs in smaller practices.

This proposed R18 addresses **AHRQ's research demonstration and dissemination priorities**, particularly around prevention and care management, with an emphasis on vulnerable groups including more rural populations (the majority of Aetna enrollees are seen in smaller practices). It also confronts unanswered organizational and financial questions raised by a recent **AHRQ report** ("A National Agenda for Research on Collaborative Care"). As one of the first cross-diagnosis CCM-based implementation studies focused on small practices, this groundbreaking study is informed by an extensive partnership with a network-model health plan (Aetna). The study also applies a novel implementation framework (REP) in which the CCM is delivered by existing providers. In addition to the specific importance of this practice-research partnership to further implement CCMs among small practices at the health plan level within a natural experiment setting, this study will contribute to the evolution of the business case for CCMs in general, enhance the utility of plan-level panel management focused on vulnerable populations across different treatment settings, and inform remote technologies that will facilitate emerging healthcare initiatives (e.g., accountable care organizations, health IT).

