## V. Methodology

**Overview.** We will conduct an RCT of the **CCM** for mood disorders vs. an educational mailing control (**EC**). The population of interest will be Aetna adult enrollees and family members (beneficiaries) across the country hospitalized for an episode of unipolar depression or bipolar disorder and belonging to a solo (i.e., single provider) or small practice (2-3 providers). Patients will be randomized to CCM or EC. The CCM will be implemented using Enhanced REP (76, 77, 79) as we have in prior studies (72, 73, 76). CCM care management will be fully remote from practice venues and patients, implemented by Aetna care managers. CCM and EC strategies represent add-ons to ongoing practice, which will not otherwise be altered. Main outcomes include mood symptoms (e.g., PHQ-9) and health-related quality of life (SF-12), accounting for nesting of patients within practices.

**C.5.b. Sample recruitment, eligibility, enrollment (Figure 2).** The following steps will be taken to enroll participants, provide informed consent, and randomize them. Participant recruitment and treatment will utilize existing Aetna resources.

[figure not shown]
1. Aetna care managers will recruit participants by first screening them based on near-real time information of recent hospitalizations (as with the pilot study). At hospitalization, Aetna is notified for (pre)authorization, typically before or within 48 hours of admission. Care managers will be notified about patient hospitalizations via the Aetna care management registry, eTUMS (Section C.5.c) and will contact the potential participant by phone as in the pilot study (Section C.4.a). Care managers will screen for eligibility and obtain informed consent and authorization to release information to the research team and to coordinate care with their providers. This will be done over the telephone after verbally explaining the protocol, risks, benefits, and safety measures via written script based on previous RCTs (92, 93). Because patients have not been randomized at this point, Aetna care managers will be blind to treatment assignment at baseline.

2. Patient inclusion criteria as determined by the care managers include:

- a. Adult patients age 21 years or older from the contiguous United States (lower 48 states)
- b. Currently covered by Aetna’s HMO or preferred provider products (for whom Aetna provides mental and medical inpatient, outpatient, and pharmacy benefits) for at least 6 months

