Missing Data: We attained subject retention of 80% over a three-year follow-up in one study (50, 51), and recent 1-year data (MH0745409) indicate 90% retention. Extent and pattern of missingness will be examined for outcome variables as well as for baseline covariates. We expect missingness to be completely at random or at random, in which case the proposed analytical methods will give unbiased estimates of treatment comparison. We will examine how sensitive our conclusions are to potential non-ignorable missingness using a pattern mixture model that will allow us to either model the observed pattern of missingness or change the imputations to represent the likely differences in conditional distributions between observed and missing data (128, 129). For the latter, we will combine the results from each imputed data using Rubin's rules (130).

**Aim 1 primary outcomes (H1a: symptoms, quality of life):** Primary outcomes are continuous, and based on pilot data, are expected to be normally distributed. If a continuous outcome exhibits a significant lack of normality, other options will be considered including data transformation, categorization, and non-parametric analyses. Four linear mixed-effects models accounting for clustering will be run to assess the CCM effects compared to EC on changes in PHQ-9, ISS, and SF-12 PCS and MCS scores over 12-months, adding baseline values of the outcome measure, the effect of CCM, time, and CCM X time interaction.

**Aim 1 secondary analyses:** For guideline concordance and hospitalization, we will compare the likelihood of receiving the guideline-concordant treatment over 12 months (Table 5) as well as the likelihood of an ambulatory care sensitive admission using a generalized linear mixed-effects model (GLM) with logit link. Similar to our primary hypotheses, linear mixed-effects models will be conducted to determine the effect of CCM vs. EC on changes in the Work and Social Adjustment Scale.

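### The either/or primary hypothesis is tested on four scores with no multiplicity rule and no deciding contrast, so a false claim of benefit has an estimated 4–10% chance instead of 2.5%

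*Combined protocol and SAP*

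**What the plan says.** Section II (Specific Aims) states the primary hypothesis as a choice: compared with education control, "the mood CCM will result in a) reduced mood symptoms in 12 months, or b) improved health-related quality of life". Aim 1 sets the comparison at 12 months.

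C.5.g (Analyses, Aim 1 primary outcomes) tests this with one model per score: "Four linear mixed-effects models accounting for clustering will be run to assess the CCM effects compared to EC on changes in PHQ-9, ISS", SF-12 PCS and SF-12 MCS. Each model is built by "adding baseline values of the outcome measure, the effect of CCM, time, and CCM X time interaction". Surveys "will be collected from patients via phone at baseline, 6, 12, 18, and 24 months thereafter", so two follow-up visits fall within the 12-month window.

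The primary list is not the same throughout:

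- Section V, Overview: "Main outcomes include mood symptoms (e.g., PHQ-9) and health-related quality of life (SF-12", with no mention of ISS.
- Table 5: "Mood symptoms: PHQ-9" and SF-12, again without ISS.
- C.5.f, text under Table 5: "changes in mood symptoms based on the PHQ-9 (102, 103) or ISS", with the SF-12 mental and physical scores.
- C.5.g: all four scores.

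The only significance level is in C.5.i (Sample Size and Power): two-sided 0.05 for a single comparison.

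**The concern.** When success on either of two domains counts, and a domain may be measured by two scores, each extra score is another chance of a false positive. Nothing in the plan limits how those chances add up. Nor does it say which coefficient or contrast supplies the p-value for a score, so a reader cannot tell beforehand which result will decide the trial.

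The trial's own pilot shows that the choice of score can matter. In Table 3 (60 patients), PHQ-9 change gave p=.17, the PHQ-9 response definition p=.04 and ISS well-being p=.02. C.5.I makes wider training of care managers conditional on the programme being proven effective, so what counts as proof should be settled first.

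**Working it through.** **1. The plan's own figure.** C.5.i gives D=.36, 90% power, two-sided 0.05, ICC 0.05 and 2 patients per practice.

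- n per arm = 2(1.960+1.282)²/0.36² = 162.2, rounded up to 163.
- Design effect = 1+(2−1)×0.05 = 1.05, and 163×1.05 = 171.15.
- This gives 86 practices, or 172 patients, per arm and 344 in total.

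The plan's number is therefore the size for one test at 0.05, before any dropout.

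**2. Error with several scores, one test each at 0.05.** With independent scores:

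- Two-sided: 1−0.95^k = 9.8%, 14.3% and 18.5% for k=2, 3 and 4.
- Benefit direction: 1−0.975^k = 4.9%, 7.3% and 9.6%.

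With a common correlation ρ, the chance of no two-sided rejection is the integral over a standard normal u of [Φ((1.96−√ρ·u)/√(1−ρ)) − Φ((−1.96−√ρ·u)/√(1−ρ))]^k. The benefit version drops the second term. The documents give no correlations, so ρ is assumed. Entries are two-sided error / false benefit.

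| Scores | ρ=0 | ρ=0.3 | ρ=0.5 | ρ=0.7 |
|---|---|---|---|---|
| 2 (one per domain) | 9.8% / 4.9% | 9.5% / 4.8% | 9.1% / 4.5% | 8.3% / 4.2% |
| 3 (PHQ-9, PCS, MCS) | 14.3% / 7.3% | 13.6% / 6.8% | 12.5% / 6.3% | 10.9% / 5.5% |
| 4 (C.5.g) | 18.5% / 9.6% | 17.4% / 8.7% | 15.6% / 7.8% | 13.0% / 6.5% |

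Against 5% and 2.5%, these run from about 1.7 times nominal (8.3/5; 4.2/2.5) to about 3.9 times (9.6/2.5). At ρ=0.9 the two-sided error is still 7.0% for two scores and 9.4% for four. An unequal pattern (PHQ-9 with MCS 0.7, PCS with MCS 0.05, others 0.1 to 0.5) gives 16.2% for four scores.

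**3. What if the term is also left open?** Suppose either of two uncorrelated model terms could count at 0.05. The error becomes 1−(1−p)², where p is the two-sided figure above.

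- Two scores: 1−(1−0.083)² = 16% to 1−(1−0.098)² = 19%.
- Four scores: 1−(1−0.130)² = 24% to 1−(1−0.185)² = 34%.

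**4. Error and power under Holm.** At the first step each score is tested at 0.05/k. With independent scores and one contrast each, two-sided error is 1−0.975² = 4.94% for two and 1−0.9875⁴ = 4.91% for four.

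For power, take 12-month completers: 172×0.8 = 137.6 per arm, and 137.6/1.05 = 131.0 effective. Power = Φ(D√(131.0/2) − z), with z = 1.960, 2.241 and 2.498.

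| Effect for one named score | 0.05 | 0.025 (two scores) | 0.0125 (four scores) |
|---|---|---|---|
| D=.36 (pilot ISS well-being) | 83% | 75% | 66% |
| D=.22 (pilot PHQ-9, absolute value) | 43% | 32% | 24% |

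Table 3 gives no SF-12 effect.

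**The case against.** Four points can fairly be made for the plan.

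*Separate hypotheses.* C.5.g refers to primary hypotheses in the plural, so limbs a) and b) may be meant as two claims reported separately, and no sentence says that the trial succeeds if any score does. This reading is open, although the Aim 1 analysis paragraph puts both limbs under the single label H1a. It lowers the figure but does not remove the problem. Each hypothesis then has up to two scores (PHQ-9 and ISS; PCS and MCS), with 8.3–9.8% two-sided error within each.

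*The time point is given.* This stands. A reader might infer that the plan leaves the time point open, but Aim 1 names 12 months. What is missing is whether the CCM effect, the interaction or a 12-month contrast decides.

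*Nobody proposes choosing between terms.* This also stands. A reader might infer a plan to take the better of two terms and quote the 16–34% in step 3. That is only a what-if: the plan leaves the term unnamed but does not propose such a choice.

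*The primary lists are closer than they look.* A reader might count four rival lists. The overview and Table 5 name the same instruments, and the text under Table 5 and C.5.g name the same four scores. The real conflict is whether ISS is primary, together with a loose 'or' between PHQ-9 and ISS. The ISS score is also unnamed. The pilot reports well-being, while C.5.d uses the scale for manic symptoms as well; that passage concerns care-manager calls and so does not settle the point.

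**Conclusion.** The concern holds. As written, the plan does not define when its primary hypothesis is met, and testing each score at 0.05 would inflate the error. Because the hypothesis is directional, the false-benefit rate is the most relevant figure: 4.2–4.9% for two scores, 5.5–7.3% for three and 6.5–9.6% for four, against 2.5%.

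These figures rest on three assumptions: 0.05 per score, which is inferred from C.5.i and stated nowhere as a testing rule; one test per score; and common correlations between 0 and 0.7. Higher correlations shrink the excess but do not remove it over the range checked. The figures do not cover a choice between model terms or between ISS scores, so they are not a strict upper limit.

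**What to change.** Before outcome data are examined:

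1. State one primary list, saying whether ISS is in it and, if so, which ISS score. Make Section II, the Section V overview, Table 5, the text beneath it and C.5.g agree.
2. Name one deciding contrast per score, for example the CCM minus EC difference at 12 months from the mixed model, so that each score yields one p-value. Holm protects the overall error only once this is done.
3. Apply Holm across the listed scores at overall two-sided 0.05, which keeps the 'or'. A pre-stated fixed sequence is an alternative. If a) and b) are meant as separate hypotheses, say so and control error within each. If both must succeed, write 'and' in Section II.

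The cost is wording and some power, with no extra patients. The loss in step 4 of the working is approximate, since it compares completers only and ignores baseline adjustment. It should not be judged from D=.36 alone: that is the pilot ISS well-being effect, and PHQ-9, the only mood score in Table 5, had .22. A short list or a fixed sequence limits the loss, which is a reason to settle item 1 first.
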